### Randomization

A total of 39 patients will be randomized, 27 patients to the enzalutamide + radium-223 arm and 12 patients to the control enzalutamide only arm. The Research Compliance Office will randomize patients and maintain the randomization table for this trial.

### Analysis sets

The *safety population*, which includes all subjects who receive at least one dose of study drug, will be used for the safety analysis.

The *randomized population*, which includes randomized subjects with follow up to EOT or disease progression (which ever comes earlier) will be used for the primary efficacy analysis. This population *excludes* patients enrolled prior to randomization.

The *combined population* includes all subjects treated with enzalutamide + radium-223 or enzalutamide alone with follow up to EOT or disease progression (which ever comes earlier). This population includes subjects enrolled prior to randomization with sufficient follow up. The combined population will be used for secondary and exploratory analyses.

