### 1.2 Secondary Objectives and Endpoint

To compare the following objectives between the two arms:

- 1.2.1 Time to progression in serum prostate-specific antigen (PSA), total alkaline phosphatase (ALP) concentrations, and radiological progression.
- 1.2.2 Response rates by serum PSA and total ALP concentrations.
- 1.2.3 Time to first skeletal related event.
- 1.2.4 Percent change in opioid use (morphine equivalent) during protocol treatment.
- 1.2.5 Overall Survival at 2 years post enrollment.

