## 10.2 Secondary Endpoint Analyses

All other statistical analyses will be descriptive in nature. Exploratory comparisons may be made between treatment arms of the randomized population. For all analyses of the combined population each treatment arm will be analyzed separately. In general, summary statistics (n, mean, standard deviation, median, minimum, and maximum for continuous variables, and number of subjects and percentage in each category for categorical variables) will be provided. Time to event variables will be summarized using Kaplan-Meier curves, and their medians will be estimated using the Kaplan-Meier method.

Additionally, source data for summaries will be presented as subject data listings. The details for analyses will be specified in the SAP.

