### Secondary and Exploratory Variables

The exploratory variables include:

- rPFS
- Time to radiological bone progression
- Total ALP response rate
- Time to total ALP progression
- Percentage change in total ALP
- PSA response rate
- Time to PSA progression
- Time to first skeletal related event (as defined below)
- OS for 2 years after enrollment
- Percent change in opioid requirement (in morphine equivalent) during protocol treatment.

Skeletal related events include the following:

- Time to occurrence of first use of external beam radiotherapy to relieve skeletal symptoms
- Time to occurrence of first tumor related orthopedic surgical intervention
- Time to occurrence of first spinal cord compression
- Time to occurrence of first new symptomatic pathological bone fractures (vertebral and non-vertebral)

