### 10.3 Exploratory Analyses

Exploratory analyses will be performed on the combined population. For additional exploratory purposes, Kaplan-Meier curves and estimates will be presented for time to event variables (rPFS, time to radiological bone progression, time to total ALP progression, time to PSA progression, OS, time to first SRE).

Frequencies and percentages will be provided for categorical variables (total ALP response rate, PSA response rate, pain response rate). Summary statistics (n, mean, standard deviation, median, minimum, and maximum) will be presented for continuous variables (percentage change in total ALP).

Further details, including handling missing data and additional censoring details, will be described in the SAP.

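### The sets used for overall survival require follow-up to EOT or progression and do not say that death satisfies this, so an early death could fall outside the OS estimate (minor)

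*Combined protocol and SAP*

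**What the plan says.** Section 10 (Analysis sets) defines two efficacy sets with the same follow-up condition. The randomized population is the one "which includes randomized subjects with follow up to EOT or disease progression (which ever comes earlier) will be used for the primary efficacy analysis". The combined population "includes all subjects treated with enzalutamide + radium-223 or enzalutamide alone with follow up to EOT or disease progression (which ever comes earlier". The same paragraph lets the pre-randomization patients in only if their follow-up is sufficient, and then states: "The combined population will be used for secondary and exploratory analyses". By contrast, the safety population in the same section needs only one dose of study drug.

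Section 1.2 lists "Overall Survival at 2 years post enrollment" among the endpoints to be compared between arms, and section 10.2 repeats it as "OS for 2 years after enrollment". On method, section 10.2 says: "Time to event variables will be summarized using Kaplan-Meier curves, and their medians will be estimated using the Kaplan-Meier method". It makes these analyses descriptive, analyses each arm of the combined population separately, and permits exploratory between-arm comparisons in the randomized population. Section 10.3 says "Exploratory analyses will be performed on the combined population" and names OS among the Kaplan-Meier variables.

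On what is left open, section 10.2 sends analysis details to the SAP, and section 10.3 adds: "Further details, including handling missing data and additional censoring details, will be described in the SAP".

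**The concern.** Entry to a survival analysis set should not depend on something observed after treatment starts. Here it depends on reaching EOT or progression, and death is not named as a third way to meet the condition. A man who dies on treatment with no progression recorded would have the OS event of interest and yet not belong to the set. A man lost early would disappear instead of contributing follow-up time up to his last contact.

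What is at stake is the 2-year OS estimate in each arm and any exploratory comparison of the arms. The effect on time to PSA, ALP or radiological progression is slight, because a patient who dies or is lost early without progressing would ordinarily be censored early anyway.

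Two other inconsistencies bear on this. The documents time the EOT visit in different ways, which changes who fails the condition. They also disagree on whether survival is followed after progression.

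**Working it through.** The plan gives no event count, sample size or power for OS, so there is no stated figure to reproduce.

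**1. Route from set to estimate.** The follow-up condition defines the combined set (section 10). That set carries the secondary and exploratory analyses (section 10), and OS by Kaplan-Meier is one of them (section 10.3). No sentence exempts OS from the condition or says that death completes follow-up. Censoring rules left to the SAP act on patients already in the set, so they do not settle who is in it.

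**2. When EOT falls.** Cycles are 28 days, so C6D1 is day 1 + 5×28 = 141, and the last day of cycle 6 is 6×28 = 168.

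| Source | EOT timing | Counted from last on-time radium dose (day 141) | Counted from last enzalutamide dose (day 168) |
|---|---|---|---|
| Calendar footnote 10 | 4 weeks after C6D1 | day 169 | day 169 (fixed) |
| Calendar footnote 6 | 4 weeks after last treatment | day 169 | day 196 |
| Section 9.3.1 | 30 days after last dose | day 171 | day 198 |

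For a patient who stops both drugs after day 1, the last-treatment timing gives day 29 and the C6D1 timing gives day 169, a gap of 140 days. Under every definition, a death on treatment comes before EOT.

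**3. Effect of a dropped death.** Assume 2-year status is known for everyone and let S be the true 2-year OS. Dropping d early deaths from n patients changes S to S×n/(n−d). The range for S is an assumption.

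| n | d | S = 40% | S = 70% |
|---|---|---|---|
| 35 (combination arm, combined set) | 1 | 0.40×35/34 − 0.40 = +1.2 points | 0.70×35/34 − 0.70 = +2.1 points |
| 35 | 2 | 0.40×35/33 − 0.40 = +2.4 | 0.70×35/33 − 0.70 = +4.2 |
| 12 (control arm) | 1 | 0.40×12/11 − 0.40 = +3.6 | 0.70×12/11 − 0.70 = +6.4 |

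For scale, the standard error at S = 50% is √(0.25/35) = 8.5 points and √(0.25/12) = 14.4 points. Each shift in the table is within one standard error.

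**4. Effect of a dropped early loss.** This can go the other way. Suppose that in an arm of 12 one man dies first and another is then lost. Keeping the lost man gives a first Kaplan-Meier step of 11/12 = 91.7%. Dropping him gives 10/11 = 90.9%. The condition as a whole therefore does not act purely upward, although dropping deaths does.

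**5. Survival follow-up.** Section 6.6 requires withdrawal from the trial, covering both treatment and follow-up, at progression or when anti-cancer therapy outside the protocol is required. Section 9.4.1 follows every patient for 2 years for OS whatever the date of progression. Section 4.4 and calendar footnote 11 also run to 2 years or death. As written, section 6.6 cannot be followed together with the others.

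**6. Missed marker tests.** Section 10.1.1 excludes a patient after two missed tests, in wording that could mean two in a row or two further misses. If it means two in a row, a man who missed C3D1 and C5D1 is excluded although he has both values that the ANCOVA uses. The cost is negligible. With a difference of 1.14, residual SD 1.14×√(1−0.50²) = 0.987, two-sided 0.05 and a noncentral t with n−3 degrees of freedom, power is 89.9% at 27/12, 89.6% at 26/12 and 88.1% at 27/11. These are ANCOVA figures, not the 85% that section 10 states for a two-sample t-test.

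**The case against.** The best reply is that the documents already treat death as the end of follow-up. Section 4.4 follows patients for two years or until death, calendar footnote 11 does the same, and section 6.6 lists death among the reasons that participation ends. On that view, a man who dies has complete follow-up and belongs in the set. This is a reasonable guess at the intent and it limits how far the point can be pressed. It does not close the gap, because the set definition names only EOT and progression.

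A second reply is that the SAP will cover this. Section 10.2 defers analysis details broadly, and no separate SAP is among the documents reviewed, so a repair may exist there. But section 10 fixes the sets itself and does not leave membership open.

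Third, the randomized set is assigned to the primary marker analysis, where needing a follow-up value is natural. Section 10.2 only permits other comparisons in it. That is right, and the main exposure is through the combined set.

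A reader might infer that a large share of deaths would be lost. Exponential survival with the medians quoted in section 3.1.4 (14.9 months) and Table 6 (18.4 months) gives 22.8% and 18.9% dying before day 169, or 8.0 and 6.6 of 35. Those are all early deaths, progressed or not. Only those without documented progression would be dropped, the documents give no such share, and eligibility requires a life expectancy of at least 6 months. The figures are a ceiling under that model, not an estimate.

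**Conclusion.** The point stands as a minor one. As worded, the sets permit early deaths without documented progression to be left out of OS, and early losses to be left out instead of censored. Each dropped death raises 2-year OS by about 1.2 to 2.1 points at n=35 and 3.6 to 6.4 points at n=12, assuming true 2-year OS between 40% and 70% and complete 2-year status. How many patients would be affected is unknown and probably small, and it depends partly on which EOT timing applies.

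The documents do not support saying that the OS results will be inflated, since the lenient reading may be the one intended and the net effect of the condition is not purely upward. Nor do they support saying that the primary test is compromised: OS is secondary and descriptive, and the missed-tests wording moves power by under 2 points per patient. The conflicts over survival follow-up and over EOT timing are plain on the text and need reconciling in any case.

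**What to change.** 1. In section 10, remove the follow-up condition for OS and the other time-to-event endpoints. Use all treated patients, including the 8 enrolled before randomization, for the per-arm summaries. Use all randomized patients as assigned, including any who were replaced under section 6.6, for any between-arm comparison.
2. State that every death is an OS event and that other patients are censored at last contact, or at last assessment for progression endpoints.
3. Reconcile section 6.6 with sections 4.4 and 9.4.1 and calendar footnote 11 on survival follow-up after withdrawal.
4. Reconcile the EOT timing in calendar footnotes 6 and 10 and section 9.3.1.
5. In section 10.1.1 and the Study Summary, state that a randomized patient with a baseline and an EOT or progression N-telopeptide value stays in the ANCOVA.

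The cost is wording in the Study Summary and sections 6.6, 8, 9.3.1 and 10. No samples are added. Survival contact about every 8 weeks is already scheduled for treated patients, subject to item 3. Footnote 11 does not cover a patient randomized but never treated, who would be censored at last contact or need one vital-status check.

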#### 10.1 Primary Endpoint Analyses

The co-primary endpoints are efficacy, safety and feasibility:

1. The primary efficacy endpoint is the change in serum N-telopeptides from baseline to end of treatment or progression (whichever comes earlier).
2. The primary safety endpoint is grade 3 or higher non hematological adverse events. The safety population will be used for all safety analyses. Safety analyses will be stratified by treatment arm.

#### **10.1.1 Primary Bone Marker Analysis**

Concomitant treatment with radium-223 (a bone targeting agent) and enzalutamide (a tumoricidal agent) is expected to decrease the level of N-telopeptides. As mentioned in the Background Section, serum N-telopeptides levels are inversely associated with overall survival, based on data from the SWOG 0421 trial. The primary endpoint for statistical analysis for this study will be the change in log 2 N-telopeptides from baseline to EOT or at disease progression (whichever comes earlier) between the randomization groups. If a bone marker test is missed at a given time point, every effort will be made to obtain the bone marker levels as early as possible. If two subsequent bone marker tests are missed, the patient will be excluded from the analysis. Equality of the change in log2 N-telopeptides between the treatment arms will be tested using an ANCOVA model with treatment group as the primary predictor and initial log 2 N-telopeptides as adjustment variable.

As a sensitivity analysis an F-test for equality of variance of final log2 N telopeptides will be performed. If the null hypothesis is rejected at the 0.1 significance level an additional ANCOVA model allowing for unequal variances will be fit.

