Diagnosis and Main Eligibility Criteria	
 
• Histologically documented adenocarcinoma of the prostate.
 
• Metastatic disease as evidenced by bony metastases on baseline bone scan and / or computed tomography (CT) scan or MRI of the abdomen and pelvis.
 
• Castration resistant prostatic adenocarcinoma. Subjects must have castrate levels of testosterone (< 50 ng/dL) achieved by orchiectomy or LHRH agonist or antagonist therapy.
 
• Evidence of disease progression on or after the most recent systemic treatment.
 
• Prior chemotherapy with docetaxel and cabazitaxel allowed.
 
• No known brain metastases, malignant pleural effusions, or malignant ascites.
 
• No visceral metastases
 
• No prior treatment with radium-223 or enzalutamide.
 
• No pathologic long-bone fractures, imminent pathologic long-bone fracture (cortical erosion on radiography > 50%) or spinal cord compression.
 

Study Product, Dose, Route, Regimen and Duration	
Combination Arm: Radium Ra 223 dichloride 55 kBq/kg body weight every 4 weeks with daily enzalutamide 160 mg PO for 6 cycles (each cycle comprises 4 weeks).
 
Control Arm: Single agent enzalutamide 160mg PO daily for 6 cycles.

Statistical Methodology	
Primary Bone Marker Analysis
 
Concomitant treatment with radium-223 (a bone targeting agent) and enzalutamide (a tumoricidal agent) is expected to decrease the level of N-telopeptides. As mentioned in the Background Section, serum N-telopeptides levels are inversely associated with overall survival, based on data from the SWOG 0421 trial. The primary endpoint for statistical analysis for this study will be the change in log 2 N-telopeptides from baseline to EOT or at disease progression (whichever comes earlier) between the randomization groups. If a bone marker test is missed at a given time point, every effort will be made to obtain the bone marker levels as early as possible. If two subsequent bone marker tests are missed, patient will be excluded from the analysis for the primary endpoint. Equality of the change in log2 N-telopeptides between the treatment arms will be tested using an ANCOVA model with treatment group as the primary predictor and initial log 2 N-telopeptides as adjustment variable. As a sensitivity analysis an F-test for equality of variance of final log2 N telopeptides will be performed. If the null

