A subject who, for any reason (e.g. failure to satisfy the selection criteria), terminates the study before the time point used for the definition of "dropout" (see above) is regarded a "screening failure".

Patients withdrawn prior to the C3D1 blood draw or determined to be not evaluable for the primary objectives may be replaced per investigators discretion.

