## 8 STUDY CALENDAR

1 cycle = 28 days

- 1 ALL Pre-study / Screening procedures should be completed within 4 weeks of study enrollment - with the exception of laboratory tests which need to be completed within 2 weeks prior to study enrollment.
- 2 Hematology includes CBC with differential and platelets. CBC must be completed within 2 weeks of study enrollment and prior to treatment ( $\pm$  7 days) on day 1 of each cycle.
- 3 Chemistry includes Albumin, Alkaline Phosphatase, Aspartate Aminotransferase, Alanine Aminotransferase, Total Bilirubin, Calcium, Carbon Dioxide, Creatinine, Chloride, Glucose, Potassium, Protein, Sodium, and Urea Nitrogen.
- 4 Bone alkaline phosphatase (BAP) should be done every four weeks until the end of treatment visit or disease progression (whichever comes earlier).
- 5 PSA is required within 28 days at screening, on day 1 of each cycle and at the end of treatment visit. PSA laboratory assessments should be performed every 4 – 6 weeks after the end of treatment visit until disease progression, or the start of another treatment.
- 6 CT and bone scans should be conducted at screening, end of cycle 3 (prior to C4D1 treatment), and at the end of treatment visit (4 weeks post last treatment). Follow-up scans will be performed as clinically indicated until documented PD per treating clinician or until the start of another treatment. Scans should include CT scan of abdomen and pelvis. Imaging of the chest is only required if clinically indicated.
- 7 Bone markers collected at baseline (C1D1), C3D1, C5D1, EOT and at disease progression (whichever comes earlier); to include procollagen Type 1 intact N-terminal Propeptide (NTP) and resorption (N-telopeptide [NT], C-Telopeptide beta-cross linked [CTB] and pyridinoline).
- 8 Radium Ra 223 dichloride 55 kBq/kg\*\* on day 1 of every cycle for up to 6 cycles (\*\* 50 kBq/kg prior to implementation of the NIST update).
- 9 Enzalutamide 160 mg daily.
- 10 End of Treatment visit should be conducted 4 weeks post C6D1.
- 11 For all patients who receive study treatment, follow-up for survival will occur approximately every 8 weeks following end of treatment or as clinically indicated for up to 2 years post enrollment or death.
- 12 All procedures for day 1 of each treatment cycle have a  $\pm$  7 day window.
- 13 Subjects receiving concomitant medication with warfarin should have INR monitored more frequently as clinically indicated.

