### Determination of sample size of the randomized cohort

Serum N-telopeptides levels are inversely associated with overall survival, based on data from the SWOG 0421 trial. The primary endpoint for statistical analysis for this study will a comparison of the change in N-telopeptides from baseline to EOT or at disease progression (whichever comes earlier) between the randomization groups. The change in log 2 N-telopeptides will be compared to the change in a control group treated with enzalutamide alone using an ANCOVA model with the final value as response, treatment group as predictor and initial log 2 N-telopeptides as an adjustment variable. Based on the data from the SWOG 0421 study, the estimated baseline mean and standard deviation of log2 N-telopeptides are 3.95 nM and 1.14 nM respectively. We further assume the Pearson correlation of baseline and follow up N-telopeptides is 0.50. With these assumptions, and with 27 evaluable patients in the radium-223 + enzalutamide arm and 12 evaluable patients in the enzalutamide only arm there will be 85% power to detect a difference of 1.14 in the change in log 2 N-telopeptides between treatment arms using a two-sample t-test at the two-sided 0.05 significance level.

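### The two-missed-tests rule can drop a randomized patient from the primary N-telopeptide analysis although both values that make up the endpoint were measured

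*Combined protocol and SAP*

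**What the plan says.** Section 10.1.1 defines the primary endpoint as "the change in log 2 N-telopeptides from baseline to EOT or at disease progression (whichever comes earlier", compared between the randomized groups. The sample size paragraph of Section 10 specifies an "ANCOVA model with the final value as response, treatment group as predictor and initial log 2 N-telopeptides as an adjustment variable". The Study Calendar (Section 8, footnote 7) gives the draws: "Bone markers collected at baseline (C1D1), C3D1, C5D1, EOT and at disease progression (whichever comes earlier". C3D1 and C5D1 therefore lie between the two values that form the endpoint.

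On missed draws, Section 10.1.1 asks for every effort to recover a missed test and then states: "If two subsequent bone marker tests are missed, the patient will be excluded from the analysis". The Study Summary ties this to the primary analysis: "If two subsequent bone marker tests are missed, patient will be excluded from the analysis for the primary endpoint". The same rule appears again for the additional analyses, in Section 10.1.2 and in the matching part of the Study Summary.

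The Analysis sets paragraph of Section 10 describes the set for the main comparison as one "which includes randomized subjects with follow up to EOT or disease progression (which ever comes earlier) will be used for the primary efficacy analysis". It sets no condition on intermediate draws and does not mention the exclusion rule. Section 6.6 adds that patients "determined to be not evaluable for the primary objectives may be replaced per investigators discretion".

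**The concern.** The rule counts draws that the primary analysis does not use. A patient with C1D1 and EOT samples but neither C3D1 nor C5D1 supplies everything the ANCOVA needs. He has follow-up to EOT, so he is in the randomized population, yet the rule takes him out of the analysis.

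Two things are at stake. First, complete primary data are discarded because of attendance after randomization, which randomization does not protect, in a comparison with only 12 controls. Second, once such a patient counts as not evaluable, Section 6.6 leaves his replacement to the investigator's discretion. The trial is open label, so that choice can be made with the arm known.

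**Working it through.** **Inputs**
- Draws: C1D1, C3D1, C5D1, EOT or progression (Section 8).
- Endpoint and model: baseline and final value only (Sections 10.1 and 10.1.1; sample size paragraph).
- Arms: "27 evaluable patients in the radium-223 + enzalutamide arm and 12 evaluable patients in the enzalutamide only arm", 39 in all.
- Difference 1.14, SD 1.14, correlation 0.50, two-sided 0.05 (sample size paragraph).
- Allowance for inevaluable patients: 50 − 47 = 3 (Section 4.2).
- Rate of missed draws: not given. I assume m = 5%, 10% or 20% per draw, independent and equal in both arms.

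**The plan's own figure.** The plan attaches no number to this rule. The nearest is the stated 85% power.
- SD of change = 1.14 × √(2 × (1 − 0.5)) = 1.14. With 27 v 12, the two-sample t-test (noncentral t, 37 df) gives 80.1%.
- ANCOVA residual SD = 1.14 × √(1 − 0.5²) = 0.987. With 36 df this gives 89.9%.

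Neither equals 85%. That is a separate matter and this point does not depend on it.

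**Step 1: which patterns matter.** Four draws give 16 missed/obtained patterns, and 8 of them contain at least two adjacent misses:

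| Missed draws | Baseline and EOT both present? |
|---|---|
| C3D1, C5D1 | Yes |
| C1D1, C3D1 | No |
| C5D1, EOT | No |
| C1D1, C3D1, C5D1 | No |
| C1D1, C3D1, EOT | No |
| C1D1, C5D1, EOT | No |
| C3D1, C5D1, EOT | No |
| All four | No |

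The rule changes who is analysed in one pattern only. In the other seven the endpoint is already missing, unless a progression sample stands in for EOT. For a patient who progresses early, the text does not say whether draws no longer due count as missed.

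**Step 2: expected number.** With baseline taken as obtained, p = P(miss C3D1 and C5D1, have EOT) = m²(1 − m).

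| m | p | 39 × p | 12 × p (controls) | P(at least one control) = 1 − (1 − p)¹² |
|---|---|---|---|---|
| 5% | 0.0024 | 0.09 | 0.03 | 2.8% |
| 10% | 0.0090 | 0.35 | 0.11 | 10.3% |
| 20% | 0.0320 | 1.248 | 0.38 | 32.3% |

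A further factor (1 − m) for having the baseline draw lowers the middle column to 0.09, 0.32 and 1.00. Misses that cluster within patients would raise it. The documents give no basis for saying by how much.

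**Step 3: cost of a lost control, if not replaced.** The SE of the arm difference is proportional to √(1/27 + 1/n).
- n = 12: 0.3469
- n = 11: 0.3577, ratio 1.031, so 3.1% larger
- n = 10: 0.3702, ratio 1.067, so 6.7% larger

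On the plan's own inputs, 27 v 11 gives 77.7% power for the t-test (from 80.1%) and 88.1% for the ANCOVA (from 89.9%), a loss of about 2 points.

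**The case against.** **The two passages need not conflict.** A reader might infer that the rule contradicts the definition of the analysis set. The documents do not support that. The Analysis sets paragraph defines a population by follow-up, and the rule can be applied afterwards as an evaluability filter for one analysis. What stands is that the two places do not refer to each other and that the filter has no function for a two-point endpoint.

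**The intermediate draws belong to the primary objective.** Section 1.1.1 compares marker levels at C1D1, C3D1, C5D1 and EOT or progression, and Section 6.6 speaks of evaluability for the primary objectives. This is fair. But Section 10.1.1 and the Study Summary attach the rule to the N-telopeptide analysis, where those draws are not used.

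**The rule fails to catch a patient who lacks only the EOT sample.** This looks like a second fault but has no consequence. Without a final value he cannot enter the ANCOVA, with or without a rule.

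**Missed draws reflect toxicity, so the result is biased.** This is conjecture. Sections 6.6 and 7.1 keep visits on the calendar when a radium dose is delayed, other blood tests are due at the same Day 1 visits, and missed marker tests are to be recovered. Conditioning on attendance after randomization remains a weakness in principle. The documents show neither its direction nor its size.

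**Loss and replacement are not both costs for the same patient.** Replacement largely restores precision. Without replacement there is no discretionary choice. This stands.

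**'Subsequent' is undefined.** If it means two further misses after a first, then C3D1, C5D1 and EOT would all be missing and no usable EOT endpoint would be lost. That reading is less natural, but the wording does not rule it out.

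**Conclusion.** The point holds in a limited form. On the natural reading, a stated rule removes from the primary analysis a randomized patient whose baseline and EOT values both exist. This happens in one of the eight patterns with adjacent misses. The expected number is about 0.1 to 1.2 of 39, assuming independent miss rates of 5% to 20%. One unreplaced control costs 3.1% in standard error.

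The case for change therefore does not rest on lost power. It rests on three facts: the exclusion serves no purpose for this endpoint, it depends on behaviour after randomization, and it opens a discretionary replacement in an open-label trial. It should be corrected, but it does not by itself threaten the primary result.

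**What to change.** - **Analysis sets (Section 10):** define the primary set once, for example: all randomized patients with a baseline N-telopeptide value and an EOT or progression value are included in the primary bone marker analysis; missed C3D1 or C5D1 samples are not a reason for exclusion.
- **Section 10.1.1 and the Study Summary:** delete the two-missed-tests exclusion. The effort to recover missed samples can stay.
- **Section 10.1.2 and the second occurrence in the Study Summary:** make the same change, so that the primary and additional analyses do not follow different rules.
- **Section 6.6:** state that a patient with both values is evaluable for the primary bone marker endpoint and is not replaced on account of missed C3D1 or C5D1 samples.

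Deleting the rule also removes the question of what 'subsequent' means. The cost is a text amendment, with no new samples or data. It keeps patients who have both values. In exchange, a replacement who might have been enrolled for such a patient no longer would be.
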